Baseline, weekly, and follow-up surveys are enclosed. Data collection will include data to be collected in the subsequent non-inferiority trial (see Subsequent Clinical Trial Description, pages 14-16, of the grant application). In the baseline survey, participants will report relevant obstetric history,³³ pre-pregnancy weight and gestational weight gain during the index pregnancy,³⁴ contraception use, smoking/e-cigarette use, employment status, household composition, and other demographics. At each time point (baseline, 6-months, 12-months), participants will complete measures of quality of life (PROPr),^{35,36} infant feeding,^{37,38} sleep (PSQI [partial]),^{39,40} depressive symptoms (EPDS),⁴¹ and social support for weight loss.⁴² At each follow-up, participants will also be queried about incident pregnancies as part of the participant survey. At 6 months, women in both conditions will rate their satisfaction with the intervention, how likely they would be to recommend it to a post-partum friend, and how likely they would be to participate again, and group cohesion.⁴³ At 6 months, we will ask women whether they participated in other weight loss programs (online or in-person), sought weight loss support on Facebook or other online social networks,⁴⁴ and if so, to what extent and reasons they sought this support.

Data Analysis: [For all studies, specify the analytic techniques the researcher will use to answer the study questions. Indicate the statistical procedures (e.g. specific descriptive or inferential tests) that will be used and why the procedures are appropriate. For qualitative data, specify the proposed analytic approaches.]

We will use Research Electronic Data Capture (REDCap)⁴⁵ for data collection and monitoring completion of study assessments. Datasets will be exported from REDCap and merged within SAS with cost-related data. PI [name] will supervise data management and quality control. We will use NVivo 11 (QSR International, Melbourne, Australia) to manage and analyze qualitative data and SAS 9.4 (SAS Inc, Cary, NC) to analyze quantitative data.

Aim 1: Feasibility. We will examine the feasibility of recruitment (especially the proportion of women unwilling to be randomized to either condition), sustained participation, contamination, retention, and feasibility of assessment procedures, particularly measurement of cost-related data, in both treatment conditions. We will describe weight loss as an exploratory outcome.

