- Recruitment. Recruitment rates will be calculated from the number of patients approached and reasons for ineligibility and non-participation. We will report numbers and reasons for recruitment using a CONSORT diagram.^{46,47}
- Sustained participation. We will calculate sustained participation as time to last intervention session attended in the IP condition and as time to last post, comment, or reaction (based on date of last post or comment reacted to) in the Facebook condition. In the Facebook condition, we will also calculate a secondary measure of sustained participation that includes last report of lurking.²⁵
- Contamination. We will describe the proportion of participant in both treatment conditions who report participating in other weight loss programs (online or in-person), seeking weight loss support on Facebook or other online social networks⁴⁴ at 6 months. We will also describe the extent of contamination and reasons women sought these extra sources of support using survey data and qualitative data from post-intervention focus groups.
- Retention. We will calculate retention as the proportion of participants who complete the 6- and 12-month follow-up study visits in each condition and report this information using a CONSORT diagram^{46,47}
- Feasibility of assessment procedures. We will examine the extent and mechanisms of missing data on each measure to be included in the subsequent non-inferiority trial.
- Weight loss. We will calculate percent weight change at 6 and 12 months by subtracting baseline weight from follow-up weights. We will define clinically significant weight loss as $\geq 5\%$.^{29,30}

Aim 2: Intervention refinement. In post-intervention focus groups, we will solicit women's feedback on posts with low engagement, and will iteratively refine these posts to make them more engaging. We will

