Exclusion criteria. During screening procedures women who are key personnel on this study, a spouse, dependent, or relative of any key personnel, a UConn employee who reports to key personnel on this study, or a UConn student whom key personnel on this study teaches will be excluded from participation. Additionally, women who are currently pregnant or plans to conceive during the study period, current participation in a clinical weight loss program, Type 1 or 2 diabetes, medical conditions or medications

affecting weight, incapable of walking $\frac{1}{4}$ mile without stopping, pain that prevents engagement in exercise, previous bariatric surgery, planned surgery during study period, plans to move out of the area during the study period, high depressive symptoms or suicidal ideation, positive screen for binge eating disorder (BED), failure to complete the baseline survey or orientation webinar.

Participants will be withdrawn from the study if: they become pregnant, disrupt in-person groups, or repeatedly post inappropriate content on Facebook.

Potential Harms/Risks and Inconveniences: [Describe the potential risks to participants (and secondary participants, if applicable) and *steps taken to minimize risks* for each participant population. Assess the likelihood of the risk occurring and, if it were to occur, the seriousness to the participant. Types of risks to consider include, but are not limited to: physical, psychological, social, legal, employment, and financial. Also describe any anticipated inconveniences the participants may experience (time, abstention from food, etc.).]

The possible risks of this study include an injury while being physically active, possible discomfort from completing questionnaires, and breach of confidentiality. Study activities do not differ from typical everyday activities of post-partum women (e.g., interacting with others on Facebook, using a mobile app, talking to other women) and/or activities done or recommended clinically and in line with national recommendations for weight loss during the post-partum period (e.g., eating a balanced nutritious diet, regular exercise, measurement of weight) and thus does not pose more than minimal risk/ slight increase over minimal risk.

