Study title: The Healthy Moms Study: Comparison of a Post-Partum Weight Loss Intervention
Delivered Via Facebook or In-Person Groups

NCT 03700736

Statistical Analysis Plan

Date of document: 10/20/2021

Statistical Analysis

We will use Research Electronic Data Capture (REDCap) to administer participant surveys and for participant tracking and data management. We will use SAS 9.4 (SAS Institute, Inc., Cary, NC) to analyze quantitative data. Reporting of the feasibility outcomes and exploratory outcome of weight change will be descriptive (e.g., percent retention at 6 and 12 months).

Primary Outcomes: Feasibility

Examination of feasibility outcomes will inform the design of the subsequent full-scale non-inferiority trial.

Recruitment. We will report recruitment using a CONSORT diagram. We will compare yield from different recruitment approaches, and will examine whether any eligibility criteria are excluding an inordinate proportion of otherwise eligible women. In particular, we will examine the number of otherwise-eligible women excluded from participation because one or the other delivery mode is not feasible or unwillingness to be randomized to either treatment condition. If recruitment rates are lower than expected, we will adjust recruitment timelines as we plan the subsequent non-inferiority trial.

Sustained participation. We will report sustained participation in both conditions. We will modify the delivery of both intervention conditions to address logistical and other barriers to sustained participation.

Contamination. We will report the extent of contamination and reasons women sought these extra sources of support. If a significant proportion of women report seeking weight loss support from other sources, we will adapt our intervention to better meet their needs to reduce the occurrence of contamination in the subsequent trial.

Retention. We will report retention in each condition. If retention is lower than expected, we will explore reasons for drop-out and make changes to the protocol to address these challenges. We will also report the proportion of participants who become pregnant within the study period.

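### The contamination measure mixes outside weight loss support that women already used at entry with support they took up during the trial, and no planned analysis separates the two

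*Protocol*

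**What the plan says.** **Eligibility.** Among the exclusions in the protocol's Inclusion/Exclusion Criteria is "current participation in a clinical weight loss program". The term clinical is not defined. Commercial or online programs and weight loss groups on social media are not named.

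**Measurement.** The survey paragraph that closes the protocol's Design, Procedures, Materials and Methods section places the contamination items at one time point: "At 6 months, we will ask women whether they participated in other weight loss programs (online or in-person), sought weight loss support on Facebook" or on other networks, followed by how much and why. The baseline list begins "In the baseline survey, participants will report relevant obstetric history" and goes on to weight history, contraception, smoking, employment, household and demographics. The scales repeated at baseline, 6 and 12 months include one for support ("and social support for weight loss"). No question about other programs or about seeking weight loss support online is listed for baseline.

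**Analysis.** Under Data Analysis, Aim 1, the plan is: "We will describe the proportion of participant in both treatment conditions who report participating in other weight loss programs", together with "seeking weight loss support on Facebook or other online social networks", at 6 months. Extent and reasons are to be described from the survey and the focus groups. Nothing limits the count to use that began after randomization.

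**Action.** The SAP's Contamination paragraph, under Primary Outcomes: Feasibility, says that if a significant proportion seek support elsewhere, "we will adapt our intervention to better meet their needs to reduce the occurrence of contamination in the subsequent trial". It sets no threshold and draws no line between prior and new use.

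**The concern.** The entry criterion is narrower than the outcome. A woman already using a non-clinical program or an online weight loss group can enrol, change nothing, and be counted as contaminated at 6 months. The population makes this plausible. Every participant must be an active Facebook user, recruitment runs partly through social networks and local Facebook groups, and the protocol's background says many women already look to Facebook for support on health and parenting.

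What is at stake is how a primary feasibility outcome is read. The pilot exists to find changes needed before the non-inferiority trial, and the two explanations call for different changes. New uptake suggests that the intervention left a need unmet. Continuing use suggests a question about eligibility or baseline adjustment in the later trial. A single 6-month proportion cannot tell the design team which of these it faces.

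**Working it through.** **1. The plan's own figures.** There is no target, threshold or precision for contamination. The only precision figure, in Justification of Sample Size, concerns retention: 1.96 × √(0.80 × 0.20 / 36) = 0.131, which reproduces the stated ±13%. It has no bearing on this point. What is used from that section is n = 36 per condition.

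**2. What the 6-month proportion contains.** Let q be the share of women whose prior outside use continues and is reported at 6 months, and r the share of the remaining women who take up something new. Then

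observed proportion = q + (1 − q) × r, and the part due to prior users = q / [q + (1 − q) × r].

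Neither q nor r is in the documents. Both are assumptions below. All 36 women per condition are taken to answer the 6-month survey; fewer will if retention is incomplete.

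**3. No new uptake (r = 0).** The observed proportion equals q.
- q = 5%: 36 × 0.05 = 1.8, about 2 women.
- q = 25%: 36 × 0.25 = 9 women.

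**4. Some new uptake (r = 10%).**

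| q | Observed | Women of 36 | Share who are prior users |
|---|---|---|---|
| 5% | 0.05 + 0.95 × 0.10 = 14.5% | 5.2 | 0.05 / 0.145 = 34% |
| 15% | 0.15 + 0.85 × 0.10 = 23.5% | 8.5 | 0.15 / 0.235 = 64% |
| 25% | 0.25 + 0.75 × 0.10 = 32.5% | 11.7 | 0.25 / 0.325 = 77% |

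**5. Different situations, same reading.**
- q = 20%, r = 10%: 0.20 + 0.80 × 0.10 = 28%, of which prior users are 0.20 / 0.28 = 71%.
- q = 10%, r = 20%: 0.10 + 0.90 × 0.20 = 28%, of which prior users are 0.10 / 0.28 = 36%.

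Both give about 10 of 36 women (36 × 0.28 = 10.1). New uptake in the second is twice that in the first, yet the planned proportion is identical.

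**6. Whether anything else in the plan separates them.**
- The social support scale is given at baseline, but it is listed apart from the program and support-seeking items and is not part of the contamination definition.
- The pre-randomization survey is described as Facebook time measures and the randomization agreement. The weekly survey covers weight and time on Facebook.
- The extent-and-reasons questions and the focus groups could reveal earlier use, but neither document says they will be used to classify it.

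**7. What a baseline question would allow.** With q of 5-25%, r could be estimated among 36 × (1 − q) = 34 down to 27 women per condition, and q would be observed directly.

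**The case against.** **The instruments are not visible.** The screener and surveys are described as enclosed but are not in the documents, and the protocol's list of survey content may not be complete. The 6-month questions might ask only about support sought since joining, and the screener might read the clinical exclusion broadly. This stands. A reader might infer that no baseline measure exists; the documents show only that none is listed.

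**Reasons are collected.** Women are asked how much outside support they sought and why, and the SAP reports this just before its adaptation sentence. A woman continuing an earlier program could say so. This softens the point but does not remove it: no analysis uses the answers to split prior from new use, and recall at 6 months is weaker than an answer given before randomization.

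**Continuing use is real exposure.** Outside support used during the 6 months can affect weight whenever it began. A reader might infer that prior users are not truly contaminated and should be dropped from the count. The documents do not support that, and the total remains a defensible measure. The difficulty lies only in what the total is taken to mean.

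**Comparison of conditions.** A reader might also infer that chance differences in prior use would pass for arm effects. Reporting is descriptive and no between-condition test of contamination is planned. At an assumed 15% per condition, the standard error of a difference is √(2 × 0.15 × 0.85 / 36) = 8.4 points, a 95% half-width of about 16.5. A gap of two women (2/36 = 5.6 points) is well inside that. Such imbalance can affect any outcome in a pilot of this size and is no part of the point.

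**Conclusion.** The point holds as one of interpretation. As written, the 6-month contamination figure combines continuing and new outside support, no analysis divides them, and the SAP attaches an action suited mainly to new use. Under an assumed 5-25% continuing prior use, about 2 to 9 of 36 women per condition would be counted without any new uptake. With 10% new uptake, also assumed, prior users would be roughly a third to three quarters of those counted. These ranges are illustrations, since the documents give no rate for either quantity.

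The consequence is moderate. Contamination is one of several descriptive feasibility outcomes, no hypothesis test depends on it, and both conditions are asked the same questions. It would be going too far to say that the intervention will be changed for the wrong reason: the reasons data may prevent that, and the unseen survey wording may already deal with part of it. The change is still worth making, because it is cheap and bears on a decision the pilot was set up to inform.

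**What to change.** - **Baseline survey.** Ask the 6-month program and support-seeking items at baseline too, or confirm that they are already there. The survey must be completed before randomization, so the answers cannot depend on allocation.
- **SAP, Contamination.** Keep total outside use over the 6 months as the headline figure. Report continuing prior use and newly started or increased use separately, by condition. Base the adaptation step on the new or increased component.
- **Eligibility.** Leave the pilot's criterion unchanged. Use the baseline proportion to inform eligibility or baseline adjustment in the later trial. Any wider exclusion there has to be weighed against recruitment, since the SAP itself will check for criteria that exclude too many women.
- **If baseline collection is finished.** The SAP is dated 10/20/2021, so this may be the case. Then state the limitation in the SAP, classify prior use from the reasons and focus-group data where possible, and add the baseline items to the later trial.

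The cost is a few survey items and a short addition to the SAP. The one drawback is a slight chance that asking at baseline prompts some women to seek other support.

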6-month follow-up assessment. At 6 months, women will participate in an in-person focus group session. We will email participants a link to complete an online survey before this visit. The survey will be administered via REDCap. Research staff will measure participants' weight individually as women are arriving for the focus group. We will ask participants in both treatment conditions to elaborate on what motivated or hindered participation. Focus groups with women in the Facebook condition will explore their reactions to and ratings of the format of low or high engagement posts (same procedures as the pre-trial focus group in Phase 1). For participants unable to attend the focus group session, we will schedule individual follow-up assessments and will conduct an individual interview (in-person or via phone) following the content of the focus group guide. We will audiotape the focus group and individual interviews. When scheduling the 6-month assessment, we will remind participants that we will audiotape the focus groups. For participants who are not comfortable with this discussion being audiotaped, we will schedule an individual visit and take notes during the interview. For follow-up assessments (both 6-month and 12-month), participants who are not willing to attend an in-person visit will be asked to self-report their current weight, and those who do not complete the survey online will be offered the option of completing the survey via phone. We expect that this study visit will take 1-1.5 hours and the survey will take 30-45 minutes. We will email participants a \$40 gift card after they complete the study visit and survey.

Due to weather or to prevent spread of illness (e.g., coronavirus), we may hold the focus group discussions via video or telephone conference call. In this case, participants would complete ratings of intervention posts via online survey. In the case of remote focus groups, we would ask participants to self-report their weight and not require in-person visits.

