12-month follow-up assessment. 12-month individual follow-up visits will include measurement of weight. Research staff will provide participants with instructions on how to remove the My Fitness Pal and time-tracking apps from their phones, and will assist participants with removal of these apps if desired. We will email participants a link to complete the survey at home following the 12-month follow-up study visit. The survey will be administered via REDCap. We expect that the survey will take about 30 minutes, and the visit will take about 15-45 minutes. We will email participants a \$40 gift card after they complete the study visit and survey.

Due to weather or to prevent spread of illness (e.g., coronavirus), we may participants to self-report their weight and not require in-person visits.

For all study assessments, research staff will call subjects who do not attend their scheduled in-person study visit to reschedule. Calls will follow the same calling procedures as the eligibility screen (see Eligibility Screen). We will reschedule the study visit a maximum of 5 times, with a maximum of 5 calls per scheduled visit before considering the woman lost to follow-up. Women who do not complete the online surveys will be sent two reminder emails containing a personalized link, at least 24 hours apart. After 7 days, research staff will may participants who have not completed the measures online to provide the participant the option of completing any remaining measures over the phone. Calls will follow the same calling procedures as the eligibility screen (see Eligibility Screen).

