This research does not involve more than minimal risk/slight increase over minimal risk. As described above, we will take steps to minimize these risks. Participants may derive direct benefit from participation. Additionally, results are intended to benefit future populations of post-partum women.

Economic Considerations: [Describe any costs to the participants or amount and method of compensation that will be given to them. Describe how you arrived at the amount and the plan for compensation; if it will be prorated, please provide the breakdown. Experimental or extra course credit should be considered an economic consideration and included in this section. Indicate when participants will receive compensation.]

Facebook, My Fitness Pal, and time-tracking apps we will recommend do not cost any money to use. We will encourage participants to check their data usage plan to ensure they are using the appropriate settings on their phone to minimize the use of their data so they don't incur any charges due to any increased use of apps during participation in the study.

Participants will receive a \$20 gift card after completing the baseline assessment (visit and survey) and a \$40 gift card after completing each follow-up study assessment (6 months and 12 months) to compensate them for their time, for a total of \$100. Participants will be reimbursed up to \$5 for parking or bus fare for each study visit (both conditions) and group intervention session (participants randomized to the in-person condition), as needed.

Data Safety Monitoring: [This is a prospective plan set up by the study investigators to assure that adverse events occurring during studies are identified, evaluated, and communicated to the IRB in a timely manner. Although the investigators initially propose a Data Safety Monitoring Plan (DSMP), the IRB must approve the plan and may require revision of the plan. A DSMP is required for all human studies at the University of Connecticut except for studies determined to be exempt from continuing IRB

review. For studies that present more than minimal risk to participants, the IRB will review and determine on a case-by-case basis whether a data safety monitoring board is most appropriate. Please refer to the IRB's policy regarding data safety monitoring *before* completing this section - <http://research.uconn.edu/policies-procedures>.

Issues that should be addressed in the DSMP include the following:

1. frequency of the monitoring

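### The withdrawal rule, as worded, takes women out of the study and not only out of the intervention, so some contamination answers (a primary feasibility outcome asked only at 6 months) may never be collected

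*Protocol*

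**What the plan says.** The withdrawal rule closes the Protocol's Inclusion/Exclusion Criteria: "Participants will be withdrawn from the study if: they become pregnant, disrupt in-person groups, or repeatedly post inappropriate content on Facebook". The Protocol does not distinguish stopping the intervention from stopping assessments, and the SAP is silent on data collection after withdrawal.

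The contamination items are placed at one time point in the Protocol's Design, Procedures, Materials and Methods section: "At 6 months, we will ask women whether they participated in other weight loss programs (online or in-person"), along with use of online networks for weight loss support. Satisfaction and group cohesion are collected at the same point: "At 6 months, women in both conditions will rate their satisfaction with the intervention". Pregnancy is asked about in the follow-up surveys: "At each follow-up, participants will also be queried about incident pregnancies as part of the participant survey".

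The 6-month survey is completed online, and "those who do not complete the survey online will be offered the option of completing the survey via phone".

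The SAP lists contamination under Primary Outcomes: Feasibility and says the intervention will be adapted if enough women report seeking support elsewhere. It gives no numerical threshold. It also plans to report the proportion who become pregnant and to explore reasons for drop-out if retention is low. The Protocol's Data Analysis section shows retention by condition in a CONSORT diagram.

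**The concern.** Neither a pregnancy nor a removal for conduct makes a woman's account of her time in the trial unusable. If the rule is applied as written, a woman withdrawn before 6 months is not asked whether she sought other weight loss support, and there is no earlier record to fall back on. The SAP ties a design decision to that proportion.

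The planned safeguards count or describe losses. Reporting the pregnancy proportion, drawing a CONSORT diagram and examining missing data cannot supply answers that were never requested. The survey needs no visit and no further intervention, so collecting it from these women is practicable. The Protocol already makes considerable efforts for other women who are hard to reach: up to five reschedulings with up to five calls each, telephone surveys and self-reported weight.

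**Working it through.** **Step 1: match the rule to the schedule.**

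- Weekly survey (Protocol, Weekly time survey): current weight and time on Facebook. No contamination item is described.
- 6-month survey: contamination, satisfaction, group cohesion, incident pregnancy.
- 6-month focus groups or interviews: the qualitative contamination data (Data Analysis, Aim 1).
- 12-month survey: incident pregnancy and the repeated questionnaires. No contamination item is described.

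The effect depends on when the event becomes known:

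| Event | Contamination answers at 6 months |
|---|---|
| Removed for conduct before 6 months | Lost on the plain reading |
| Pregnancy known before the 6-month survey | Lost on the plain reading |
| Pregnancy first reported in the 6-month survey | Not lost |
| Event after the 6-month survey | Not lost; the 12-month survey would be |

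**Step 2: the plan's own precision figure.** Justification of Sample Size gives ±13% for retention at 80% with 36 per condition. 1.96 × √(0.8 × 0.2 / 36) = 0.131, so it reproduces. The point does not dispute it.

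**Step 3: size of the loss.** The documents give no pregnancy, removal or contamination rate, so the following are assumptions:

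- 80% of 36 answer at 6 months (80% is the retention level the Protocol calls acceptable): 0.8 × 36 = 28.8, taken as 29 per condition.
- The rule removes k = 1 or 2 women per condition who would otherwise have answered.
- 30% of women report contamination.

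Share of answers lost, k/29: 1/29 = 3.4%; 2/29 = 6.9%. This is also the widest span over which the lost answers leave the proportion open, whatever the contamination rate.

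Example with k = 2: 8 of 27 is 29.6%. With both missing women included, the proportion lies between 8/29 = 27.6% and 10/29 = 34.5%, a span of 6.9 points.

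95% half-width, 1.96 × √(0.3 × 0.7 / n):

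| n | Half-width (points) |
|---|---|
| 29 | 16.7 |
| 28 | 17.0 |
| 27 | 17.3 |

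Shift in the proportion, (k/29) × the difference between lost and remaining women: k = 1 and 10 points gives 0.3; k = 2 and 30 points gives 2.1.

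**The case against.** The strongest reply is that the rule may say less than it seems to. The sentence answers a form prompt about conditions for removal from the study, so its wording may echo the template and not reflect a decision about data collection. Contact after withdrawal could be described in the consent form or grant application. This stands as a limit: a reader might infer that surveys certainly stop, but the documents only leave that as the plain reading.

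Several stronger inferences also go too far:

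- **That every pregnancy costs 6-month data.** The only stated pregnancy question after enrolment is in the follow-up surveys. Only pregnancies volunteered or raised with staff earlier, and conduct removals, cost 6-month answers.
- **That three planned outcomes are affected.** Satisfaction and group cohesion are collected but appear neither in the Aim 1 analyses nor in the SAP. Only contamination is a stated outcome.
- **That retention is distorted.** Retention is defined by completed visits, and no text removes withdrawn women from the denominator. On an all-randomized denominator the rate is the same with or without extra surveys.
- **That post-conception weights make the point more serious.** The 12-month survey comes after the weigh-in ("We will email participants a link to complete the survey at home following the 12-month follow-up study visit"), and the weight calculation ("We will calculate percent weight change at 6 and 12 months by subtracting baseline weight from follow-up weights") does not say what happens when a pregnancy is then reported. That is a missing detail on an exploratory outcome and does not support this point.

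The size objection is fair too. At 80% completion, ordinary non-response already leaves 36 − 29 = 7 women per condition unanswered (7/36 = 19.4%), far more than the rule adds. Reporting is descriptive, and with no contamination threshold no decision can be shown to change. What survives is that these answers can be collected cheaply and the wording, taken plainly, gives them up.

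**Conclusion.** The point holds as a minor one, limited to contamination. As worded, the rule ends study participation for pregnancy or conduct, and no other text in the Protocol or SAP continues follow-up. The affected women are those removed for conduct, or known to be pregnant, before the 6-month survey.

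On the assumptions shown, the proportion per condition is left open by at most 3.4 to 6.9 points, the half-width grows by 0.3 to 0.6 points, and the shift is 0.3 to 2.1 points. These figures treat every withdrawn woman as someone who would otherwise have answered, so for a given number withdrawn they are upper values. The conclusion also rests on the Protocol's description of the surveys, since the forms themselves were not available. If the consent form or grant application already provides for continued surveys, one clarifying sentence in the withdrawal rule is enough.

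**What to change.** - Reword the rule so that pregnancy or removal for conduct stops the intervention only. With consent, continue to offer the existing follow-up surveys online or by phone.
- Have these women answer the contamination items for the time up to stopping, since a woman who has stopped may have less reason to seek weight loss support. Show the contamination proportion with and without them.
- Keep visit completion among all randomized women as the retention figure set against 60% and 80%. Do not count women who give only a survey as retained.

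**Cost.** Wording changes in the Protocol, SAP and consent form, a small edit to the survey's reference period, and a rule that the "gift card after completing each follow-up study assessment (6 months and 12 months) to compensate them for their time" is paid for the survey alone. At $40 per follow-up, that is up to 2 × $40 = $80 for a woman withdrawn before 6 months and $40 for one withdrawn later. If 2 to 4 women were withdrawn in each period (an assumption), the total would be 2 × $80 + 2 × $40 = $240 to 4 × $80 + 4 × $40 = $480. No visits are added.

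**Downside.** These women's answers cover a shorter exposure and are recalled later, so they are not fully comparable with the rest; hence the two presentations. Survey and weight tables will have different denominators.
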